### Aim 2: Pilot RCT

The objective of the pilot RCT is to demonstrate (1) the feasibility of participant recruitment and retention, (2) participant acceptability of Lumen for PST, and (3) engagement of neural targets subserving emotional reactivity and cognitive control (i.e., target engagement).

**Randomization and blinding.** A designated staff person performs randomization using an online system that [name] and team published. The system is a modern implementation of Pocock and Simon's minimization, a covariate-adaptive method to achieve better-than-chance marginal balance between study arms across multiple key baseline characteristics. Minimization accommodates a greater number of balancing covariates than does stratified randomization. The system's computational algorithm automatically adjusts the randomization probability based on the characteristics of all the previously randomized participants, thus minimizing the total covariate imbalance between arms after each new participant is randomized. In this study, randomization covariates include sex, age, race/ethnicity, education, digital health literacy, PHQ9, and GAD7. Note that, aside from eligibility screening, PHQ9 and GAD7 are also process measures used to monitor treatment progress throughout PST sessions. Their inclusion among randomization covariates helps avoid accidental bias at baseline. The online system applies Efron's biased-coin method to protect allocation concealment with the use of nonextreme randomization probabilities, and the staff person(s) using the system has/have no deep knowledge of the backend coding or execution and no ability to manipulate it. By design, treatment assignments are identifiable to participants, but blinding of outcome assessment, event adjudication, and data analysis will be enforced. To accomplish the 2:1 allocation, participants are randomized into 3 sets, and then 2 of these sets will be combined to form the Lumen group. The remaining set forms the waitlist control group. This method both protects blinding and preserves the allocation ratio at every allocation as per Kuznetsova and Tymofyeyev. The same method is used in the ongoing ENGAGE-2 study.

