### Aim 2: Pilot RCT

Pilot RCT sample size calculation using a confidence interval approach: To obtain a precision interval with a standardized half-width of 0.50 (akin to a medium effect) with 90% assurance, we have planned a sample size of 60 ( $n_{Trt}=40$ ,  $n_{Con}=20$ ), assuming  $\geq 85\%$  retention at 16 weeks. This provides reliable estimates of between-treatment differences in change in amygdala activation for nonconscious threat-related reactivity and change in DLPFC activation for cognitive control from week 0 to 16 in Criterion 1. In Criterion 2, a sample size of 60 will also be sufficient to detect a correlation coefficient of  $r=0.4$  with 0.80 power and 2-sided  $\alpha=0.05$ . We are not focused on smaller correlations ( $r<0.4$ ) because their implications are likely to have more limited clinical relevance.

The criteria to evaluate neural target engagement are as follows:

**Criterion 1.** The level of task-evoked activation for either the amygdala for nonconscious threat-related emotional reactivity or for the DLPFC for cognitive control improves meaningfully from week 0 to 16 in the Lumen group compared with the waitlist control group.

Criterion 1 is tested via  $t$  test that compares the change from week 0 to 16 in the Lumen group with that change in the waitlist control group. Participants are analyzed based on the group to which they are assigned using all available data. The  $t$  test described above can be readily expanded for exploratory subgroup analyses by applying to each subgroup (e.g., female vs. male).

**Criterion 2.** Change in the level of task-evoked activation of a neural target that meets Criterion 1 correlates with temporally concurrent change from week 0 to 16 in self-reported measures within the corresponding PST theory-based construct for emotional reactivity or cognitive control. We consider correlations of  $r\geq 0.4$  meaningful.

To test Criterion 2, we examine the regression change of the amygdala activity from week 0 to 16 on change in self-reported measures of emotional reactivity (worry, affect) from week 0 to 16, controlling for baseline values of the self-reported measures and group assignment. We expect that the coefficient for the change in amygdala activation is significant and positive in the direction of improvement in its

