corresponding, validated emotional reactivity self-report measures and that this relationship may be significantly modified by group assignment. Similarly, we examine the regression change of the DLPFC activity from week 0 to 16 on change in self-reported measures of cognitive control (problem solving, dysfunctional attitudes) from week 0 to 16, controlling for baseline values of the self-reported measures and group assignment. We expect that the coefficient for the change in DLPFC activation is significant and positive in the direction of improvement in its corresponding, cognitive control validated self-report measures and that this relationship may be significantly modified by group assignment.

In addition, we will also conduct exploratory and secondary analyses. We will conduct an exploratory whole-brain analysis (1) to verify our *a priori* specification of neural targets, namely, amygdala for emotional reactivity and DLPFC for cognitive control, and (2) to identify any additional voxel clusters that are activated by our tasks and are associated with treatment response. Secondary analyses compare differences in discrete changes in PROs from week 0 to 16 and trajectories of change based on intensive time-series ecological measures between the Lumen and waitlist control groups. Analyses of the treatment effects on PROs employ the same *t* test approach as described above for testing Criterion 1 for target engagement. Furthermore, dosing analyses are conducted within the Lumen treatment group. The primary dosing analysis examines the relationship of neural target activation in the amygdala and DLPFC to the 4 measures of dose (number and length of PST sessions, fidelity-weighted number, and length of PST sessions). The secondary dosing analysis examines the relationship of patient-report outcomes, ecological end-of-day assessments, and measures of treatment progress (e.g., PHQ9 and GAD7 across PST sessions) to the same 4 measures of dose. Given neural target activation measures and PROs are obtained at weeks 0 and 16, these analyses focus on change over the full 16-week span of the study, whereas ecological end-of-day assessments and treatment progress measures are available for a total of 8 occasions each, and thus will be considered longitudinally.

Please see Appendix 3 for detailed power analysis and statistical analysis plan.

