Treatment acceptability	Session metrics : Number and duration of PST sessions completed; End-of-session Lumen user survey : NASA Task Load Index (TLX),  User Experience Questionnaire-Short version (UEQ-S),  adapted Working Alliance Inventory for digital interventions (WAI-Tech) 			NA	NA	X
Digital health literacy	Digital Health Literacy Instrument 	self-report		X	NA	NA
COVID impact	COVID impact survey 	self-report		X	NA	NA
Religious involvement	Duke University Religion Index 	Self-report		X	NA	NA
COVID impact on social functioning	COVID impact on social functioning survey	self-report		X	X	NA
Social network	Social Network Index 	Self-report		NA	NA	X
Loneliness	UCLA 3-item loneliness survey 	Self-report		NA	NA	X
Height	Height	Measured		X	NA	NA
Weight	Body weight	Measured		X	X	NA
Blood pressure	Blood pressure	Measured		X	X	NA
Sociodemographics	age, sex, race, ethnicity, education, race, ethnicity, income, household size, marital status, employment status, occupation, smoking/vaping	self-report		X	NA	NA
Adverse Events (AE)	AE form	Interview		X	X	NA

aTo minimize missing data, participants will receive \$50 at wk 0, study iPad (unlocked) or \$100 (if opting out iPad) at wk 16, and \$1 per daily diary.

bHADS is used as the independent outcome measure of depressive and anxiety symptoms at weeks 0 and 16. PHQ9 and GAD7 are used for 2 purposes: (1) eligibility screening (before week 0) and (2) treatment progress monitoring across PST sessions (in weeks 1, 2, 3, 4, 6, 8, 10, 12).

cIn addition to ecological daily assessments that will occur for 7 days at weeks 0 and 16, they also will occur every 2 weeks (on weeks 2, 4, 6, 8, 10, 12). During active treatment in the Lumen arm (Studies 1 & 2) or the in-person PST arm (Study 2), this will occur for 3 days prior to, the day of, and 3 days after each scheduled PST session. For waitlist controls, this will occur for 7 days starting on Sunday of each assigned week.

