## Appendix 3. Power analysis and statistical analysis plan – Aim 2 Pilot RCT

### A. Power Analysis

The primary objective of the Pilot RCT in the R61 phase is to evaluate neural target engagement based on the criteria (specified in B.1 below) in order to transition to the R33 phase. Research to examine neural targets as mechanisms of psychotherapy is an emerging field. No prespecified treatment difference of clinical importance or established effect sizes are available for our proposed neural target measures from fMRI. To address such early stage research, Julious recommended that rather than powering in the traditional fashion to test a formal hypothesis of a (in truth unknown) desirable treatment difference, the sample size be selected in order to provide a given level of precision of the treatment effect estimates using the confidence interval (CI) approach, which Ma et al. have used in a completed NIH-funded pilot RCT. Specifically, Julious and others recommended the use of precision intervals of prespecified standardized width to guide sample size determination. Julious offered a further refinement to provide *Assurance* (akin to power) that a chosen standardized width of the precision interval contains the true mean treatment difference. To obtain a precision interval with a 2-sided standardized half-width of 0.5 (akin to a medium effect size) with 90% assurance, we have planned a sample size of 60 ( $n_{Trt}=40$ ,  $n_{Con}=20$ ), assuming  $\geq 85\%$  retention at 16 weeks. This will provide reliable estimates of *meaningful improvement* from week 0 to 16 in amygdala activity for nonconscious threat-related reactivity and in DLPFC activity for cognitive control among Lumen participants, compared with waitlist controls (target engagement criterion (1); see below). Tests of the 2 *a priori* neural targets—amygdala for emotional reactivity and DLPFC for cognitive control—are regarded as separate inferential domains, that is, not within one family of comparisons, and thus are not corrected for multiplicity (or familywise error rate) across domains. Importantly, as explained, the objective of the Pilot RCT is not to claim statistical significance of a prespecified key hypothesis but to obtain reliable effect estimates with precision for a decision on transition to the next phase. In this context, multiple testing is not required or recommended.

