The SPEAC project is at the frontier of research on developing a voice-based AI agent (Lumen) for PST and validating its effect on *a priori* neural targets, and the Pilot RCT (Study 1) is to estimate possible effects of target engagement, which, if promising, will support further investigation to confirm target engagement in Study 2. In this context, we apply a precision interval approach (see Section A above) to determine Criterion 1. We define that, compared with the waitlist control group, the Lumen PST treatment group will demonstrate a *meaningful improvement* in a neural target if the standardized between-group mean difference is at least Cohen's  $d=0.3$  in favor of Lumen (small effect; 50% of that in ENGAGE). At this effect size, the upper limit of the precision interval overlaps with  $d=0.8$  (large effect) given a standardized half-width of 0.5 with 90% assurance that the interval contains the true mean difference based on the power analysis. We consider such a finding to be meaningful and will suffice Criterion 1.

- ii. Criterion 2. Change in the level of task-evoked activation of a neural target that meets Criterion 1 correlates with temporally concurrent change from week 0 to 16 in self-reported measures within the corresponding PST theory-based construct for emotional reactivity or cognitive control. As noted, we consider correlations of  $r=0.4$  or greater meaningful. Specifically:
  - a. If the amygdala target exhibits a meaningful improvement in the Lumen group vs. the waitlist control (Criterion 1), then we will examine whether that improvement is significantly correlated with improvements in validated self-report measures of emotional reactivity (worry, affect) over the same 0-to-16-week interval.
  - b. If the DLPFC target exhibits a meaningful improvement in the Lumen group vs. the waitlist control (Criterion 1), then we will examine whether that improvement is significantly correlated with improvements in cognitive control (problem solving, dysfunctional attitudes) over the same 0-to-16-week interval.

Criterion 1 is tested via *t* test that compares the change from week 0 to 16 in the Lumen group with that change in the waitlist control group. Participants are analyzed based on the group to which they are assigned using all available data. The *t* test described above can be readily expanded for exploratory subgroup analyses by applying to each subgroup (e.g., female vs. male).

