### **B.2. Treatment effects on PROs and ecological measures**

Secondary analyses will compare differences in discrete changes in PROs from week 0 to 16 and trajectories of change based on intensive time-series ecological measures between the Lumen and waitlist control groups. Analyses of the treatment effects on PROs will employ the same *t* test approach as described above for testing Criterion 1 for target engagement.

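### Criterion 1 rests on an unadjusted t test of change; adjusting for the same target's baseline activation, already collected, would in most plausible settings sharpen the estimate held against d ≥ 0.3

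*Combined protocol and SAP*

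**What the plan says.** - **Test.** Section 9.0 (Aim 2) and Appendix 3 B.1 give the same analysis for Criterion 1: a t "test that compares the change from week 0 to 16 in the Lumen group with that change in the waitlist control group". No covariate is named.
- **Decision rule.** B.1 counts a target as meaningfully improved "if the standardized between-group mean difference is at least" Cohen's d of 0.3 in favour of Lumen. Either target suffices. The SD used for d is not stated.
- **Precision.** Appendix 3 A plans for a "standardized half-width of 0.5 (akin to a medium effect size) with 90% assurance", with 40 and 20 randomised and at least 85% retained.
- **Baseline data.** Appendix 2 and B.1 schedule fMRI activation at weeks 0 and 16.
- **Minimisation.** Section 6.0 says the "randomization covariates include sex, age, race/ethnicity, education, digital health literacy", PHQ9 and GAD7. No activation measure is listed.
- **PROs.** Section 9.0 states "Analyses of the treatment effects on PROs employ the same" t test approach, and Appendix 3 B.2 repeats it. Appendix 2, footnote b, adds that "HADS is used as the independent outcome measure of depressive and anxiety symptoms at weeks 0 and 16".
- **Baseline adjustment elsewhere.** The Criterion 2 regressions control for baseline self-report values, but not for baseline activation.
- **Missing data.** Appendix 3 B.4 calls linear mixed models the primary technique and analyses the imputed data sets with MIXED. It names no baseline-activation term.

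**The concern.** The outcome's own baseline enters Criterion 1 only by subtraction. Subtraction is fully efficient only when the slope of week-16 on baseline is 1. When the slope is lower, a group that starts high by chance tends to show a spuriously large fall, and the reverse for a group that starts low. Nothing in the design directly limits such imbalance in activation.

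This matters because Criterion 1 compares a point estimate with a fixed threshold. Noise in the estimate translates directly into false passes and missed passes in a rule that helps decide whether the project moves to the R33 phase. Part of that noise can be removed with data the trial already collects.

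**Working it through.** **Inputs.** From the documents: 40 and 20 randomised, 85% retention, so 34 and 17 completers; threshold d = 0.3; earlier in-person result d = 0.6 (ENGAGE). Assumed, because the documents do not give them: the week 0-to-16 correlation of activation, ρ, from 0.2 to 0.8, and the ratio of the week-16 SD to the baseline SD, k, from 0.8 to 1.4. Cohen's d is taken in SD-of-change units, the natural reading for a t test of change.

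**The plan's own figure.** SE = √(1/34 + 1/17) = 0.297. The two-sided 90% half-width is t(0.95, 49 df) × SE = 1.677 × 0.297 = 0.498, and 51/0.85 = 60. The planned sample size is therefore reproduced, provided 90% is read as the confidence level.

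**Unadjusted rule.**
- Inert target reaches 0.3: 1 − Φ(0.3/0.297) = 0.156.
- Either of two inert targets, if independent: 1 − (1 − 0.156)² = 0.288.
- True d of 0.6 reaches 0.3: Φ(0.3/0.297) = 0.844.

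**Effect of a chance imbalance.** With k = 1, a baseline difference of 0.3 SD moves the observed d by 0.3(1 − ρ)/√(2(1 − ρ)). This is 0.16 at ρ = 0.4 and 0.095 at ρ = 0.8, against a threshold of 0.3.

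**Variance with own-baseline adjustment, relative to the change score.** Ratio = [k²(1 − ρ²)/(1 + k² − 2ρk)] × (48/47), where 48/47 is the cost of estimating the slope. At k = 1 this is ((1 + ρ)/2) × (48/47).

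| k | ρ = 0.2 | 0.4 | 0.5 | 0.7 | 0.8 |
|---|---|---|---|---|---|
| 0.8 | 0.48 | 0.55 | 0.58 | 0.64 | 0.65 |
| 1.0 | 0.61 | 0.71 | 0.77 | 0.87 | 0.92 |
| 1.2 | 0.72 | 0.83 | 0.89 | 0.99 | 1.02 |
| 1.4 | 0.80 | 0.91 | 0.96 | 1.02 | 1.00 |

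**What this does to the decision.** Adjusted half-width = t(0.95, 48 df) × 0.297 × √ratio; the pass probabilities use 0.297 × √ratio as the SE.

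| Setting | 90% half-width | One inert target passes | Either inert target passes | True d = 0.6 passes |
|---|---|---|---|---|
| Unadjusted | 0.498 | 0.16 | 29% | 0.84 |
| k = 1, ρ = 0.4 | 0.42 | 0.12 | 22% | 0.88 |
| k = 1, ρ = 0.8 | 0.48 | 0.15 | 27% | 0.85 |
| k = 1.2, ρ = 0.4 | 0.46 | 0.13 | 25% | 0.87 |
| k = 1.2, ρ = 0.7 | 0.495 | 0.155 | 29% | 0.85 |

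A simulation with 40,000 trials per setting, dividing both estimates by the estimated pooled SD of change, agrees. At k = 1, ρ = 0.4, the inert-target pass rate is 0.156 unadjusted and 0.118 adjusted; at d = 0.6 the pass rates are 0.844 and 0.883.

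**Symptom PROs.** HADS measures the same constructs as PHQ9 and GAD7, which are minimised, so part of its baseline imbalance is already removed. If that part is 25%, 50% or 75% (assumed), the ratio at k = 1 is 0.77, 0.83 or 0.91 at ρ = 0.4, and 0.90, 0.93 or 0.96 at ρ = 0.7. The restricted entry range on PHQ9 and GAD7 could also make k exceed 1. The gain is therefore smaller.

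**Choice of standardiser.** If the adjusted difference were divided by the regression's residual SD, the inert-target pass rate would return to 1 − Φ(0.3/(0.297 × √(48/47))) = 0.159 at any ρ. At k = 1, ρ = 0.4, a threshold of 0.3 residual SDs is only 0.3 × √0.70 = 0.25 in SD-of-change units.

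**The case against.** The plan meets its own standard: the t test is unbiased over randomisation, and the sample size was set for this estimator and delivers the stated half-width. The benefit depends on two quantities the documents do not give. At k = 1.2 with ρ of 0.7 to 0.8 the ratio is 0.99 to 1.02, which is no gain. Elsewhere the change in pass probabilities is often modest, and the closeness of the threshold to zero comes from the point-estimate and either-target rules, which adjustment leaves in place. Criterion 2, feasibility and acceptability also bear on the transition. All of this stands. It makes the point an improvement in efficiency, not the repair of an invalid test.

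Three further objections carry less weight.

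- **The standardiser is unstated, so the 16% and 29% depend on a reading.** True. With the baseline SD and k = 1, the inert-target rate would be 0.18 unadjusted and 0.14 adjusted at ρ = 0.4, and 0.055 and 0.048 at ρ = 0.8. Adjustment still helps, and the fix names the SD.
- **B.1 also justifies 0.3 by an upper limit reaching 0.8.** That sentence is tied to the planning half-width of 0.5 and remains true as a planning statement, although the realised interval may be narrower.
- **B.4 mentions mixed models and imputed covariates.** It specifies no baseline-activation term. On complete two-visit data, a mixed model with unconstrained baseline means gives the same contrast as the t test of change.

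**Conclusion.** The concern holds. Criterion 1 uses an estimator that leaves avoidable noise in place in most of the range examined. With equal SDs at the two visits, own-baseline adjustment lowers the variance by 39% at ρ = 0.2, 29% at ρ = 0.4 and 8% at ρ = 0.8. Across the whole assumed grid the ratio runs from 0.48 to 1.02, so the possible loss is about 2% (half-width 0.503 against 0.498). Where adjustment helps, false passes fall and the chance of passing a true d of 0.6 rises. The size of the gain rests on ρ and k, which are assumptions, on 34 and 17 completers, and on d being in SD-of-change units. The case is firmest for the neural targets and weaker for the symptom PROs. The change should be made, but the planned test is not invalid.

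**What to change.** In Section 9.0 and Appendix 3 B.1 and B.2:

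1. Make the primary analysis a regression of the week-16 value (or the change) on group and the baseline value of the same outcome. A week 0/16 mixed model with a common baseline mean is an acceptable alternative.
2. Keep the 0.3 threshold. State that d is the adjusted difference divided by the pooled SD of change, not by the residual SD.
3. Report the unadjusted t test of change as a sensitivity analysis.
4. As a minor point of wording, bring the mixed-model and MIXED statements in B.4 into line with the one model named in B.1 and B.2.

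The cost is SAP wording and one of 49 degrees of freedom. No new data are needed.

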## 1.0 Project Summary/Abstract

Depression and anxiety are the leading causes of disability and lost productivity, and are often underdiagnosed and undertreated owing to access, cost, and stigma barriers. Novel and scalable psychotherapies are urgently needed. Advances in artificial intelligence (AI) offer a transformative opportunity to develop intelligent voice assistants as virtual health agents accessible on personal devices. Meanwhile, major advances in human neuroscience have fueled a paradigm shift to study brain mechanisms underlying behavioral health interventions. Leveraging emerging science in these transdisciplinary areas, this project aims to develop and rigorously test a novel voice-enabled, AI virtual agent named Lumen, trained on Problem Solving Therapy (PST), for patients with moderate, untreated depressive and/or anxiety symptoms. The project will investigate the effect of Lumen on engagement of a priori neural targets—amygdala for emotional reactivity and dorsal lateral prefrontal cortex (DLPFC) for cognitive control—as putative mechanisms. The project has 2 phases: R61 and R33 (see Figure 1). Phase 1 is the R61 phase (years 1-2) and will be the sole focus of this protocol. Focusing on Lumen development and refinement as well as pilot testing, Phase 1 has 2 specific aims. Aim 1 on Lumen development and refinement will proceed in 2 stages: (1) scenario-based clinician evaluations, and (2) a formative user study (n=30 participants). Aim 2 is to pilot test Lumen in a 2-arm randomized clinical trial (pilot RCT), among 60 participants with moderate, untreated depression and/or anxiety who are randomized in a 2:1 ratio to receive PST with Lumen (n=40) on a secure study iPad or be on a waitlist (n=20). At weeks 0 and 16 participants will complete functional magnetic resonance imaging (fMRI) to assess neural target engagement as well as validated surveys of patient-reported outcomes (PROs) (e.g., depressive and anxiety symptoms, functioning, quality of life). In addition, participants will complete ecological daily assessments of mood, stress, appraisal and coping for 7 days every 2 weeks during the 16-week follow-up period. The Phase 1 milestones are (1) establishing the functionality, usability, and treatment fidelity of Lumen; and (2) demonstrating feasibility, acceptability, and neural target engagement. Achieving these milestones will provide the basis for the future R33 phase (Phase 2) focused on examining target engagement and PROs in a larger 3-arm RCT by comparing Lumen with a waitlist control arm and an in-person PST arm. This protocol only focuses on the R61 phase.

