### B. Statistical Analysis Plan

#### B.1. Treatment effects on target engagement

Based on literature and our preliminary data, we define neural targets *a priori* as activation of the amygdala for nonconscious threat-related emotion reactivity and activation of the DLPFC for cognitive control. The activation variables are from fMRI, which will be completed at weeks 0 and 16. Also, validated self-report surveys of emotional reactivity (worry, affect) and cognitive control (problem solving, dysfunctional attitudes) will be obtained at weeks 0 and 16. These self-report measures were chosen because of prior evidence for their role mediating the effect of PST on depressive symptoms.

Note that improvement for emotional reactivity corresponds to a *decrease* in amygdala activity whereas improvement for cognitive control corresponds to an *increase* in DLPFC activity. For consistency in the presentation of analyses, the measure will be constructed such that higher positive values are better; thus, change toward a *higher value is improvement*.

Activation of either neural target satisfies 2 criteria:

- i. Criterion 1. The level of task-evoked activation for either the amygdala for nonconscious threat-related emotional reactivity or for the DLPFC for cognitive control improves meaningfully from week 0 to 16 in the Lumen group compared with the waitlist control group.

The ENGAGE Phase 1 project (UIC IRB protocol #2015-1324) showed significant improvement in amygdala activation for nonconscious threat-related emotional reactivity from baseline to 2 months, and the standardized treatment effect was Cohen's  $d=0.6$ . We also underscore that the 2-month time point in that project, which tested an integrated depression and obesity behavioral treatment, coincided with the start of weight loss treatment, which was sequenced after the first 5 PST sessions for depression, so measurements of neural targets at 2 months assessed the effect of PST alone. In ENGAGE, PST was delivered via in-person individual sessions with trained coaches.

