#### **B.4. Intention to Treat (ITT) and Handling Missing Data**

Clinical trials such as the one proposed must face the issues of dropout and missing data. We have put in place a strong plan to ensure maximum retention of participants through the course of the study, with a projected 85% or greater retention (see the *Recruitment and Retention Plan*). Data missing completely at random (MCAR) may be analyzed “as is” without imputation, as it does not introduce bias into estimates and inferences. More commonly, data are missing at random (MAR) owing to covariate-dependent events (e.g., irregular work shifts, children’s illness, transportation, and scheduling foul-ups). Our primary analysis technique, linear mixed models, is robust for MAR and provides unbiased estimates of model parameters without imputation. (One may impute as well, but the benefit is usually modestly improved power rather than changes to conclusions.) The more serious concern for behavioral interventions is the possibility that data will be missing not at random (MNAR). This occurs when dropout or missingness is related to the level of the outcome of interest (e.g., a participant’s level of depression or anxiety). If treatment is working well and symptoms of depression and anxiety have lessened, then participants may feel continuation in treatment is not necessary or beneficial. They drop out or miss sessions because the treatment seems to have worked. On the other hand, if participants experience no improvement in symptoms, they may drop out or miss sessions because they are discouraged that the treatment seems not to have worked. In either case, the loss of data is related to the outcomes under study and has the potential to bias the study’s conclusion about the intervention. Handling the problem of MNAR is difficult. First, there is no test for the presence of MNAR (*vs.* MAR). Second, there are many possible underlying sources of MNAR and there is no guarantee that explorations of missing data patterns will clearly reveal those sources. Third, missing data imputation for MNAR necessarily makes strong and untestable statistical assumptions, so that conclusions from imputed MNAR datasets must remain tentative. This picture reinforces our strong commitment to participant retention (see the Study 1 *Recruitment and Retention Plan*).

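### The only subgroup method stated for Lumen versus waitlist is a t test within each subgroup; no estimate or interval for the difference between subgroups is planned

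*Combined protocol and SAP*

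**What the plan says.** Criterion 1 compares the week 0 to 16 change in amygdala or DLPFC activation between Lumen and waitlist by a t test. Section 9.0 (Aim 2) and Appendix 3, B.1 then say, in the same words, that this test "can be readily expanded for exploratory subgroup analyses by applying to each subgroup (e.g., female vs. male". Appendix 3, B.2 uses the same t test approach for the patient-reported outcomes.

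Two other places mention interaction or effect modification, and neither covers this contrast:

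- Appendix 3, B.3.c adds baseline characteristics, with sex as one example, and their interactions with dose. Those analyses run only within the Lumen arm, so they carry no information on whether the difference from waitlist varies by sex.
- The Criterion 2 regressions allow group assignment to modify the association between brain change and self-report change. That is not a subgroup effect.

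Appendix 3, A frames the pilot as estimation with stated precision, not as a claim of statistical significance.

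**The concern.** Female versus male names a comparison, but a t test in women and another in men do not make it. Each asks whether Lumen differs from waitlist in that sex. If one is significant and the other is not, the cause may be a difference in effect, unequal numbers or chance, and the two results do not say which. The quantity that answers the question is the difference between the two subgroup effects, with its interval, and the plan does not ask for it.

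What is at stake is interpretation. Small subgroups make discordant results common even when the effect is identical, and a reader of the pilot report could take such a result as a sign that Lumen works in one sex only.

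**Working it through.** **Inputs from the documents**

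- Sample: "we have planned a sample size of 60" (40 Lumen, 20 waitlist), Appendix 3, A.
- Retention: "with a projected 85% or greater retention", Appendix 3, B.4. 60 x 0.85 = 51 completers, 34 + 17.
- Effect sizes, Appendix 3, B.1: d=0.3 is the Criterion 1 threshold; d=0.6 is the amygdala effect reported from ENGAGE.
- Sex is a minimization covariate (Section 6.0), so roughly 2:1 within each sex is reasonable.

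**Assumptions not in the documents**

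- Two-sided alpha 0.05 for Criterion 1 (the plan gives alpha only for the Criterion 2 correlation).
- Sex split of 50:50 or 70:30.

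**Step 1. The plan's own figure.** Section 9.0 states its target as "To obtain a precision interval with a standardized half-width of 0.50 (akin to a medium effect) with 90% assurance". Half-width = t(0.95, df) x sqrt(1/nT + 1/nC). With 34 + 17 and df = 49 this is 0.498, so the stated 0.50 is reproduced if 90% assurance is read as a 90% interval. The plan gives no figure for subgroups. The same formula within subgroups gives 90% half-widths of 0.55 to 0.97 SD.

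**Step 2. Chance that exactly one sex is significant in favor of Lumen when the true effect is the same in both.** For each sex, p is the noncentral t probability of exceeding the upper critical value, with noncentrality d / sqrt(1/nT + 1/nC). The two sexes are independent, so

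P(exactly one) = p1(1 - p2) + p2(1 - p1).

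Example, 51 analyzed, split about 70:30 (24 + 12 and 10 + 5), d=0.6: p1 = 0.378, p2 = 0.173, and 0.378 x 0.827 + 0.173 x 0.622 = 0.420.

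| Analyzed, split | Subgroup sizes (Lumen + waitlist) | d=0 | d=0.3 | d=0.6 |
|---|---|---|---|---|
| 60, 50:50 | 20+10, 20+10 | 0.049 | 0.200 | 0.436 |
| 60, 70:30 | 28+14, 12+6 | 0.049 | 0.201 | 0.460 |
| 51, about 50:50 | 17+9, 17+8 | 0.049 | 0.182 | 0.401 |
| 51, about 70:30 | 24+12, 10+5 | 0.049 | 0.183 | 0.420 |

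**Step 3. Hypothetical: the d>=0.3 rule applied within each sex.** The plan does not state this. If it were done, exactly one sex would pass in 35-38% of trials at true d=0, 50% at d=0.3 and 34-37% at d=0.6.

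**Step 4. What an interaction estimate would deliver.** SE = sqrt of the sum over sexes of (1/nT + 1/nC), in SD units.

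- Best case (60, 50:50): sqrt(2 x (1/20 + 1/10)) = sqrt(0.300) = 0.55.
- Worst case (51, about 70:30): sqrt(1/24 + 1/12 + 1/10 + 1/5) = sqrt(0.425) = 0.65.
- Difference detectable with 80% power: (1.96 + 0.84) x SE = 1.53 to 1.83 SD.
- 95% half-width: 1.10 to 1.31 SD.
- Power for a true difference of 0.6 SD: 15% to 19%.

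Under the same assumptions the interaction test signals a difference that is not there in 5% of trials.

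**The case against.** The case against giving this much weight is strong in several respects, and most of it stands.

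- *The wording is permissive.* The test can be expanded, and the work is labelled exploratory. A reader might infer that a pass in one sex and a fail in the other will be declared effect modification. The documents state no such rule, no subgroup hypothesis and no subgroup alpha.
- *The d>=0.3 threshold belongs to the whole-trial comparison.* A reader might infer that it carries over to each sex. The plan extends the t test, not the threshold, so Step 3 is only a what-if.
- *Discordance depends on the true effect.* The 40-46% range uses the ENGAGE effect, which came from in-person delivery. At half that effect the range is 18-20%, and with no effect it is about 5%.
- *No consequence is documented.* A reader might infer that a false sex signal would shape the larger Study 2. Transition rests on feasibility, acceptability and the two whole-trial criteria; nothing ties subgroup results to the design of Study 2.
- *The interaction gains little power.* For a two-level subgroup the single model gives the same mean differences as separate comparisons, apart from the pooled residual variance, and a non-significant interaction can itself be misread as showing no difference.

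What does not stand is that the exploratory label makes the method suitable. An estimation pilot should report the quantity of interest with its precision. Two t tests leave the reader to derive it, and their significance labels invite the wrong comparison.

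**Conclusion.** The point holds as a limited one. The plan names a specific method for subgroup differences in the Lumen versus waitlist contrast. That method does not address whether the effect differs, and nothing elsewhere in the plan fills the gap.

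Under the assumptions listed, an identical true effect would look sex-specific by significance in roughly one trial in five at d=0.3 and two in five or more at d=0.6. The problem is mainly the splitting of a real shared effect, since the rate is about 5% when there is none. Criterion 1, Criterion 2 and every milestone are unaffected.

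The correction improves the inference and makes the imprecision visible. It does not make the pilot able to detect plausible subgroup differences.

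**What to change.** In Section 9.0 (Aim 2) and Appendix 3, B.1, replace the subgroup sentence with:

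> Exploratory subgroup effects are estimated in one model on all participants containing group, the subgroup variable and their interaction. The interaction estimate and its confidence interval are reported, labelled exploratory, with subgroup-specific estimates and intervals from the same model. A difference between subgroups is not inferred from one subgroup test being significant and the other not, and a non-significant interaction is not read as showing no difference.

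Add a short statement of expected precision: for a two-level subgroup such as sex, an SE of about 0.55 to 0.65 SD, so that only differences of about 1.5 to 1.8 SD are detectable with 80% power, with the assumed subgroup split and alpha given.

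The cost is a few lines of text in two places and one model term. No new data are needed, and the whole-trial Criterion 1 analysis is unchanged. The remaining risk, that a wide interaction interval is taken as evidence of no difference, is covered by the last sentence of the replacement text.
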